### EXPLORATORY EFFICACY ANALYSES

The following efficacy variables are considered exploratory:

- Platelet count and change from baseline in platelet count at each visit
- Proportion of subjects who achieve platelet count of  $\geq 50 \times 10^9/L$ ,  $\geq 75 \times 10^9/L$ , or  $\geq 200 \times 10^9/L$  at each visit
- Number of platelet units used per platelet transfusion episode
- Severity of bleeding events assessed by WHO bleeding score and BARC bleeding scale
- Proportion of subjects with a WHO bleeding score  $\geq 2$  after randomization and up to 7 days following an elective procedure (revised per Amendment 04)

In general, the continuous variables will be analyzed within an analysis of covariance framework or Wilcoxon rank sum test, as appropriate. Categorical variables will be analyzed using CMH, Chi-square or Fisher's exact test. Additional analysis may be performed as needed using appropriate statistical methodologies as specified in the SAP.

Subgroup analyses will be performed on the primary efficacy variable, including age group ( $< 65$  and  $\geq 65$  years old); sex (male and female); race (white, black, asian and other); geographic region; bleeding risk associated with the elective procedure (low, moderate, or high based on Amendment 02 categorization); MELD score ( $< 10$ , 10-14, and  $> 14$ ); and CTP grade (A, B, and C). Additional subgroups may be explored, if deemed appropriate.

No adjustment for multiplicity is planned for exploratory, subgroup and sensitivity analyses.

### 9.7.1.7 Pharmacokinetic, Pharmacodynamic, and Pharmacogenomic/Pharmacogenetic Analyses

#### **PHARMACOKINETIC ANALYSES**

Plasma concentration versus time data will be listed. The data will be analyzed using a population PK approach to estimate population PK parameters and the effect of covariates on the PK parameters will be evaluated.

For the population PK analysis, data from this study will be pooled with PK data from two Phase 2 studies in subjects with thrombocytopenia associated with liver disease, including hepatitis C, and possibly with data from Phase 1 studies.

The population PK analysis will be performed to characterize the PK of avatrombopag in subjects with thrombocytopenia associated with liver disease, and to screen for potential covariates with any significant and clinically relevant effects on avatrombopag PK. The PK model will be parameterized for absorption rate constant, apparent clearance, and apparent volume of distribution. Derived exposure parameters will be area under the concentration-time curve and maximum plasma concentration.

#### **PHARMACOKINETIC/PHARMACODYNAMIC ANALYSES**

The relationship between avatrombopag concentration and platelet count will be analyzed using a population PK/PD approach to estimate population PD parameters and the effect of covariates on the PD parameters will be evaluated.

For the PK/PD modeling, data from this study will be pooled with PK/PD data from two Phase 2 studies in subjects with thrombocytopenia associated with liver disease, including hepatitis C, and possibly with data from Phase 1 studies.

The population PK and PK/PD analyses will be detailed in a separate analysis plan.

#### **PHARMACOGENOMIC/PHARMACOGENETIC ANALYSES**

Not applicable

### 9.7.1.8 Safety Analyses

All safety analyses will be performed on the Safety Analysis Set. Safety assessment will be summarized for overall and within each baseline platelet count cohort as appropriate. Safety assessments including AEs, laboratory tests, vital signs, and ECG will be summarized by treatment groups using descriptive statistics (mean, standard deviation, median, minimum and maximum) or frequency count as appropriate. No hypothesis testing will be performed for safety assessment.

Study Day 1 for all safety analyses will be defined as the date of the first dose of study drug.

## EXTENT OF EXPOSURE

The extent of exposure to study drug will be characterized by duration of exposure (in days) for each treatment group.

Duration of exposure will be defined as the number of days between the date the subject received the first dose of study drug and the date the subject received the last dose of study drug. Duration of exposure will be summarized using descriptive statistics by treatment group. In addition, the duration of exposure will be categorized and will be summarized using frequency count by treatment group.

## ADVERSE EVENTS

The AE verbatim descriptions (investigator terms from the CRF) will be classified into standardized medical terminology using the Medical Dictionary for Regulatory Activities (MedDRA). Adverse events will be coded to the MedDRA (Version 15.1 or higher) lower level term closest to the verbatim term. The linked MedDRA preferred term (PT) and primary system organ class (SOC) are also captured in the database.

A treatment-emergent AE (TEAE) is defined as an AE that emerges during treatment (up to 30 days after the last dose of study drug), having been absent at pretreatment (Baseline) or

- Reemerges during treatment (up to 30 days after the last dose of study drug), having been present at pretreatment (Baseline) but stopped before the last dose of study drug plus 30 days, or
- Worsens in severity during treatment (up to 30 days after the last dose of study drug) relative to the pretreatment state, when the AE is continuous.

Only those AEs that were treatment emergent will be included in summary tables. All AEs, treatment emergent or otherwise, will be presented in subject data listings.

Treatment-emergent AEs will be summarized by treatment group. The following summaries will be reported for TEAEs:

- Incidence of TEAEs by SOC and PT
- Incidence of treatment-related TEAEs by SOC and PT
- Incidence of TEAEs by SOC, PT, and CTCAE Grade
- Incidence of TEAEs by SOC, PT, and relationship to treatment.

A subject will be counted only once within a SOC and PT, even if the subject experienced more than 1 TEAE within a specific SOC and PT.

The following summaries will also be presented for the treatment-emergent SAEs:

- Incidence of treatment-emergent SAEs by SOC and PT
- Incidence of treatment-related treatment-emergent SAEs by SOC and PT
- Incidence of treatment-emergent SAEs by SOC, PT, and relationship to treatment

In addition, subjects with TEAEs, treatment-related TEAEs leading to discontinuation from study treatment, and AEs of special interest for this study (including recurrence of thrombocytopenia, thromboembolic events and bleeding events [WHO Grade 2 to 4]) will also be summarized for each treatment group.

### LABORATORY VALUES

Laboratory results will be summarized using Système International units, as appropriate. With the exception of urinalysis, platelet function tests, and platelet count (which is considered as an efficacy parameter), for all quantitative parameters listed in [Section 9.5.1.5 Safety Assessments \(Laboratory Measurements\)](#), the actual value and the change from baseline to Procedure Day and to the end of the Follow-up Phase will be summarized by treatment group using descriptive statistics. Analysis of changes from baseline will be based on the number of subjects with both nonmissing baseline and relevant postbaseline results.

Laboratory test results will be assigned a low/normal/high (LNH) classification according to whether the value was below (L), within (N), or above (H) the laboratory parameter's reference range. Shifts from baseline (LNH) to Procedure Day and to the end of the Follow-up Phase will be presented for each laboratory parameter. Similar shift tables from baseline (LNH) to the highest/lowest postbaseline LNH classification will also be provided.

[Appendix 1 \(Sponsor's Grading for Laboratory Values\)](#) presents the criteria that will be used to identify subjects with treatment-emergent markedly abnormal laboratory values (TEMAV). Except for phosphate, a TEMAV is defined as a postbaseline value with an increase from baseline to a grade of 2 or higher. For phosphate, a TEMAV was defined as a postbaseline value with an increase from baseline to a grade of 3 or higher. The number and percentage of subjects with TEMAVs will be presented by treatment group; each subject may be counted once in the laboratory parameter high and in the laboratory parameter low categories, as applicable. Markedly abnormal laboratory values will be flagged in the subject data listings.

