**Table 4 Clinical Laboratory Tests**

Category	Parameters
Hematology	
Complete Blood Count	hematocrit, hemoglobin, platelets, RBC count, and WBC count with differential (basophils, eosinophils, lymphocytes, monocytes, total neutrophils [segmented and bands])
Coagulation panel	prothrombin time, activated partial thromboplastin time, international normalized ratio
Chemistry	
Electrolytes	bicarbonate, chloride, potassium, sodium
Liver function tests	alanine aminotransferase, alkaline phosphatase, aspartate aminotransferase, direct bilirubin, total bilirubin, gamma-glutamyl transpeptidase
Renal function parameters	blood urea nitrogen, creatinine
Other	albumin, calcium, cholesterol, creatine phosphokinase with fractionation, globulin, glucose, lactate dehydrogenase, phosphorus, total protein, triglycerides, uric acid
Urinalysis	bacteria, casts, crystals, epithelial cells, glucose, ketones, occult blood, pH, protein, RBCs, specific gravity, WBCs
Protocol specified	
Females only	serum beta-human chorionic gonadotropin pregnancy tests, urine pregnancy tests
Platelet function tests a	eg, p-selectin and integrin IIbβ3 with and without an agonist. The following agonists will be used: 0.5 μM ADP, 20 μM ADP, 1.5 μM TRAP, or 20 μM TRAP (eg, platelet aggregation with an agonist. ADP will be used as the agonist) (revised per Amendment 02)

ADP = adenosine diphosphate, RBC = red blood cell, TRAP = thrombin receptor agonist peptide, WBC = white blood cell

a: Performed only at selected sites

Clinical laboratory tests during the study will be performed by the designated central laboratory. All blood and urine samples will be collected and sent to the central laboratory on the day of collection unless otherwise instructed. When a hematology test is required, 2 blood samples will be collected: 1 for central laboratory analysis and 1 for local laboratory analysis. Investigators will utilize the platelet count result received from the local laboratory hematology test analysis to qualify subject's entry into the study, and also for clinical assessments.

Only platelet count data from local laboratories, including the date and clock time of collection of the sample, will be collected and entered into the CRF for analysis. All other hematological parameters will be collected and loaded into the database for analysis according to results derived from the designated central laboratory.

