#### **REPORTING OF SIGNIFICANT LABORATORY ABNORMALITY**

Any significant treatment-emergent laboratory abnormality observed during the clinical study should be entered on the Adverse Event CRF and reported using the procedures detailed in Reporting of Serious Adverse Events ([Section 9.5.4.1](#)), even if the laboratory abnormality does not meet serious criteria. If the significant laboratory abnormality does not meet serious criteria, it must still be reported using the SAE form and in an expedited manner but should be noted as nonserious on the SAE form and the Adverse Event CRF.

A laboratory result should be considered a treatment-emergent significant abnormality if the result:

- Is within normal limits at baseline and has increased in severity to meet the sponsor's grading criteria for laboratory values of Grade 3 or above
- Is outside normal limits at baseline and increases in severity to the sponsor's grading criteria for laboratory values of Grade 4 or above. These abnormalities are automatically considered to be serious, with the exception of expected and reproducible hematologic abnormalities.
- Is otherwise considered by the investigator to meet serious criteria as defined in [Section 9.5.1.5](#) (Serious Adverse Events and Other Events of Interest)

Significant laboratory abnormalities should not be listed as separate AEs or SAEs if they are considered to be part of the clinical syndrome that is being reported as an AE or SAE.

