## 12 APPENDICES

## Appendix 1 Sponsor's Grading for Laboratory Values

(revised per Amendment 02)

Sponsor's Grading for Laboratory Values				
	Grade 1	Grade 2	Grade 3	Grade 4
BLOOD/BONE MARROW				
Hemoglobin	< LLN – 10.0 g/dL < LLN – 100 g/L < LLN – 6.2 mmol/L	< 10.0 – 8.0 g/dL < 100 – 80 g/L < 6.2 – 4.9 mmol/L	< 8.0 g/dL < 80 g/L < 4.9 mmol/L; transfusion indicated	life-threatening consequences; urgent intervention indicated
Leukocytes (total WBC)	< LLN – 3.0 x 10  /L < LLN – 3000/mm 	< 3.0 – 2.0 x 10  /L < 3000 – 2000/mm 	< 2.0 – 1.0 x 10  /L < 2000 – 1000/mm 	< 1.0 x 10  /L < 1000/mm 
Lymphocytes	< LLN – 800/mm  < LLN – 0.8 x 10  /L	< 800 – 500/mm  < 0.8 – 0.5 x 10  /L	< 500 – 200/mm  < 0.5 – 0.2 x 10  /L	< 200/mm  < 0.2 x 10  /L
Neutrophils	< LLN – 1.5 x 10  /L < LLN – 1500/mm 	< 1.5 – 1.0 x 10  /L < 1500 – 1000/mm 	< 1.0 – 0.5 x 10  /L < 1000 – 500/mm 	< 0.5 x 10  /L < 500/mm 
Platelets	< LLN – 75.0 x 10  /L < LLN – 75,000/mm 	< 75.0 – 50.0 x 10  /L < 75,000 – 50,000/mm 	< 50.0 – 25.0 x 10  /L < 50,000 – 25,000/mm 	< 25.0 x 10  /L < 25,000/mm 
METABOLIC/LABORATORY				
Albumin, serum- low (hypoalbuminemia)	< LLN – 3 g/dL < LLN – 30 g/L	< 3 – 2 g/dL < 30 – 20 g/L	< 2 g/dL < 20 g/L	life-threatening consequences; urgent intervention indicated
Alkaline phosphatase	> ULN – 3.0 x ULN	> 3.0 – 5.0 x ULN	> 5.0 – 20.0 x ULN	> 20.0 x ULN
ALT	> ULN – 3.0 x ULN	> 3.0 – 5.0 x ULN	> 5.0 – 20.0 x ULN	> 20.0 x ULN
AST	> ULN – 3.0 x ULN	> 3.0 – 5.0 x ULN	> 5.0 – 20.0 x ULN	> 20.0 x ULN
Bicarbonate, serum-low	< LLN – 16 mmol/L	< 16 – 11 mmol/L	< 11 – 8 mmol/L	< 8 mmol/L
Bilirubin (hyperbilirubinemia)	> ULN – 1.5 x ULN	> 1.5 – 3.0 x ULN	> 3.0 – 10.0 x ULN	> 10.0 x ULN
Calcium, serum-low (hypocalcemia)	< LLN – 8.0 mg/dL < LLN – 2.0 mmol/L	< 8.0 – 7.0 mg/dL < 2.0 – 1.75 mmol/L	< 7.0 – 6.0 mg/dL < 1.75 – 1.5 mmol/L	< 6.0 mg/dL < 1.5 mmol/L
Calcium, serum-high (hypercalcemia)	> ULN – 11.5 mg/dL > ULN – 2.9 mmol/L	> 11.5 – 12.5 mg/dL > 2.9 – 3.1 mmol/L	> 12.5 – 13.5 mg/dL > 3.1 – 3.4 mmol/L	> 13.5 mg/dL > 3.4 mmol/L

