5.2.4 Demographic and Other Baseline Characteristics

Demographic and other baseline characteristics for the FAS and Safety Analysis set will be summarized for each treatment group and overall using descriptive statistics or frequency count. Continuous demographic variables include age, weight, height and body mass index (BMI); categorical variables include age group (<65, and ≥ 65 years old), sex, ethnicity, race, region and country. The following baseline disease characteristics will also be summarized:

- Baseline platelet count and its category ($<40 \times 10^9/L$ and 40 to $<50 \times 10^9/L$)
- Bleeding risk associated with the elective procedure (low, moderate and high based on Amendment 02 categorization) and the type of elective procedure
- HCC status (yes and no) and Barcelona-Clinic Liver Cancer (BCLC) stage (0, A, B, C and D)
- Model for End-stage Liver Disease (MELD) score
- Child-Turcotte-Pugh (CTP) score and CTP grade (A, B and C)
- Baseline international normalized ratio (INR) and its category (≤ 1.6 and >1.6)
- Portal vein flow rate as per Doppler Sonography assessment
- Creatinine clearance and disease etiology.

MEDICAL HISTORY

All medical histories as documented by the Investigator will be coded using the Medical Dictionary for Regulatory Activities (MedDRA).

The number (percentage) of subjects reporting a history of any medical condition will be summarized by System Organ Class (SOC), preferred term for each treatment group and overall based on FAS.

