12 REFERENCES

13 APPENDICES**13.1 Sponsor's Grading for Determining Markedly Abnormal Laboratory Results**

	Grade 1	Grade 2	Grade 3	Grade 4
BLOOD/BONE MARROW				
Hemoglobin	< LLN – 10.0 g/dL < LLN – 100 g/L < LLN – 6.2 mmol/L	< 10.0 – 8.0 g/dL < 100 – 80 g/L < 6.2 – 4.9 mmol/L	< 8.0 g/dL < 80 g/L < 4.9 mmol/L; transfusion indicated	life-threatening consequences; urgent intervention indicated
Leukocytes (total WBC)	< LLN – 3.0 x 10 ⁹ /L < LLN – 3000/mm ³	< 3.0 – 2.0 x 10 ⁹ /L < 3000 – 2000/mm ³	< 2.0 – 1.0 x 10 ⁹ /L < 2000 – 1000/mm ³	< 1.0 x 10 ⁹ /L < 1000/mm ³
Lymphocytes	< LLN – 800/mm ³ < LLN – 0.8 x 10 ⁹ /L	< 800 – 500/mm ³ < 0.8 – 0.5 x 10 ⁹ /L	< 500 – 200/mm ³ < 0.5 – 0.2 x 10 ⁹ /L	< 200/mm ³ < 0.2 x 10 ⁹ /L
Neutrophils	< LLN – 1.5 x 10 ⁹ /L < LLN – 1500/mm ³	< 1.5 – 1.0 x 10 ⁹ /L < 1500 – 1000/mm ³	< 1.0 – 0.5 x 10 ⁹ /L < 1000 – 500/mm ³	< 0.5 x 10 ⁹ /L < 500/mm ³
Platelets	< LLN – 75.0 x 10 ⁹ /L < LLN – 75,000/mm ³	< 75.0 – 50.0 x 10 ⁹ /L < 75,000 – 50,000/mm ³	< 50.0 – 25.0 x 10 ⁹ /L < 50,000 – 25,000/mm ³	< 25.0 x 10 ⁹ /L < 25,000/mm ³
METABOLIC/LABORATORY				
Albumin, serum- low (hypoalbuminemia)	< LLN – 3 g/dL < LLN – 30 g/L	< 3 – 2 g/dL < 30 – 20 g/L	< 2 g/dL < 20 g/L	life-threatening consequences; urgent intervention indicated
Alkaline phosphatase	> ULN – 3.0 x ULN	> 3.0 – 5.0 x ULN	> 5.0 – 20.0 x ULN	> 20.0 x ULN
ALT	> ULN – 3.0 x ULN	> 3.0 – 5.0 x ULN	> 5.0 – 20.0 x ULN	> 20.0 x ULN
AST	> ULN – 3.0 x ULN	> 3.0 – 5.0 x ULN	> 5.0 – 20.0 x ULN	> 20.0 x ULN
Bicarbonate, serum-low	< LLN – 16 mmol/L	< 16 – 11 mmol/L	< 11 – 8 mmol/L	< 8 mmol/L
Bilirubin (hyperbilirubinemia)	> ULN – 1.5 x ULN	> 1.5 – 3.0 x ULN	> 3.0 – 10.0 x ULN	> 10.0 x ULN
Calcium, serum-low (hypocalcemia)	< LLN – 8.0 mg/dL < LLN – 2.0 mmol/L	< 8.0 – 7.0 mg/dL < 2.0 – 1.75 mmol/L	< 7.0 – 6.0 mg/dL < 1.75 – 1.5 mmol/L	< 6.0 mg/dL < 1.5 mmol/L

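### PT, INR and aPTT are measured but not graded, so the plan gives no between-arm count of marked coagulation worsening

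*Protocol*

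**What the plan says.** Protocol Table 4 lists a coagulation panel: "prothrombin time, activated partial thromboplastin time, international normalized ratio". Table 5 schedules it at Screening, Procedure Day (Visit 4) and Day 35 (Visit 6).

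The grading table is protocol Appendix 1, "Sponsor's Grading for Laboratory Values", repeated in SAP 13.1 as "Sponsor's Grading for Determining Markedly Abnormal Laboratory Results". Two sets of rules draw on it directly:

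- **Marked abnormality (protocol 9.7.1.8, SAP 5.6.3).** Appendix 1 "presents the criteria that will be used to identify subjects with treatment-emergent markedly abnormal laboratory values (TEMAV"). Except for phosphate, which uses Grade 3, "a TEMAV is defined as a postbaseline value with an increase from baseline to a grade of 2 or higher".
- **Expedited reporting of a significant laboratory abnormality (protocol 9.5.4.3).** The first criterion covers a result that is normal at baseline and "has increased in severity to meet the sponsor's grading criteria for laboratory values of Grade 3 or above". The second covers a result abnormal at baseline that rises to Grade 4. The third does not need a grade: "Is otherwise considered by the investigator to meet serious criteria as defined in" the section on serious events.

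Protocol 9.7.1.8 and SAP 5.6.3 also provide descriptive summaries of values and changes from baseline, and low/normal/high shifts for each laboratory parameter to Procedure Day, to the end of follow-up, and to the highest and lowest post-baseline class. SAP 5.2.4 tabulates "Baseline international normalized ratio (INR) and its category", split at 1.6, among the baseline characteristics only.

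**The concern.** The drug raises platelet counts in patients with liver disease before a procedure. Rescue for bleeding is part of the primary endpoint, and bleeding and thromboembolism are events of special interest. Coagulation status is relevant background to both, and the documents single out INR. It is one of the three laboratory components of MELD (protocol 9.5.1.2), and the cut-off of 1.6 appears in protocol 9.1.2.3 and again in SAP 5.2.4.

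The TEMAV table is the one display meant to count subjects, by arm, whose result became markedly worse. A test without a grade row cannot enter it. If the SAP is followed exactly, a reader of the study report could see the average INR change and the extremes by arm, but not how many subjects in each arm worsened substantially. SAP 13.1 is a fixed list, so the analysts would have no reason to add the missing tests themselves.

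**Working it through.** The check is a comparison of tables and rules. The plan states no figure to reproduce.

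**1. Rows in the grading tables.**
- Blood/bone marrow: hemoglobin, leukocytes, lymphocytes, neutrophils, platelets = 5.
- Metabolic/laboratory: albumin, alkaline phosphatase, ALT, AST, bicarbonate, bilirubin, calcium low, calcium high, cholesterol, creatinine, GGT, glucose high, glucose low, phosphate, potassium high, potassium low, sodium high, sodium low, triglyceride, uric acid = 20.
- Total 5 + 20 = 25 in protocol Appendix 1, and the same 25 in SAP 13.1. Rows for PT, INR or aPTT: 0 in each. The two copies agree and both run through to their footnotes, so a row lost in text extraction is unlikely.

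**2. Which rules need a row.**

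| Route | Needs a grade row? | Reaches coagulation? |
|---|---|---|
| TEMAV table and listing flag | Yes | No |
| Expedited criterion 1 (to Grade 3 or above) | Yes | No |
| Expedited criterion 2 (to Grade 4) | Yes | No |
| AE for a rise of 2 or more CTCAE grades (9.5.1.5) | Unclear: stated in CTCAE grades, but points to Appendix 1 | Arguable |
| Expedited criterion 3 (investigator judges serious criteria met) | No | Yes |
| AE because the abnormality led to an intervention (9.5.1.5) | No | Yes |
| AE because the investigator judges an out-of-range value to be one (9.5.1.5) | No | Yes |
| Values and change from baseline by visit, with minimum and maximum (SAP 5, 5.6.3) | No | Yes |
| Low/normal/high shifts (SAP 5.6.3) | No | Yes, with a ceiling |

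**3. The ceiling in the shift table.** High is the top class. A subject above the reference range at baseline who rises further moves from High to High. The shift to the highest post-baseline class has the same limit. Protocol 7.2.1 describes prolonged PT, aPTT and INR as a recognised finding in cirrhosis, so a High baseline may be common. The documents give no proportion.

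**4. The other MELD components.** MELD uses bilirubin, creatinine and INR. Appendix 1 grades bilirubin and creatinine. INR is the only one of the three without a row.

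**5. What is left for a between-arm count.** The descriptive summaries give means, medians and ranges, not numbers of subjects with marked worsening. The shifts count subjects but stop at High. Reported AEs depend on treatment given or on judgement at each of about 80 to 100 sites. None of these yields a count against a fixed severity limit.

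**The case against.** A reader might infer that worsening coagulation can never be flagged in this trial. The documents do not support that. Coagulation is in the by-visit summaries, whose maximum would show an extreme INR, and in the shift tables. An abnormality that leads to an intervention is an AE whether or not it has a grade. Protocol 9.1.2.3 speaks of treating subjects with INR above 1.6 where indicated, so a rise that leads to such treatment already falls under the intervention rule. The third expedited criterion also remains open. Nor can it be said that the TEMAV table will print zero for coagulation in both arms: the table shells are in a separate document, and an ungraded test may simply be absent. All of this stands.

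A reader might also want a number. With an assumed 50% to 90% of subjects High at baseline, the shift ceiling would apply to 0.5 × 133 = 66.5 (about 67) to 0.9 × 133 = 119.7 (about 120) of the planned avatrombopag subjects, and to 0.5 × 67 = 33.5 (about 34) to 0.9 × 67 = 60.3 (about 60) on placebo. The documents give no basis for that range, and the counts describe where subjects start, not how many worsen or are missed.

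Three further objections have weight:

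- Other Table 4 tests, such as LDH, CPK and blood urea nitrogen, have no row either, so the list is selective by design. INR differs because the plan itself gives it a category and uses it in MELD.
- Thromboembolic events and WHO Grade 2 to 4 bleeding are reported and tabulated directly, and protocol 7.2.1 says that thrombotic tendency is raised in cirrhosis despite prolonged coagulation times. The clinical outcomes therefore do not depend on a laboratory flag.
- A ≤1.6 / >1.6 shift has its own ceiling: a rise from 1.7 to 3.5, as an illustration, would not register. It needs a companion summary.

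**Conclusion.** The point holds as a gap in the display of safety data. PT, INR and aPTT are collected but ungraded, so they are outside the TEMAV table and the first two expedited criteria. They are covered only by descriptive change, by shifts that cannot show worsening from a High baseline, and by AE reporting that rests mainly on intervention or judgement.

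The size is unknown, because the baseline INR distribution is not given. The conclusion rests on two readings: that the 25-row tables are complete as printed, and that a parameter without a row cannot generate a TEMAV. Whether the 2-grade AE rule reaches coagulation depends on whether its authority is CTCAE itself or Appendix 1, which the text leaves open.

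The primary and secondary endpoints, the alpha control and the sample size are unaffected. This is a cheap improvement to the safety analysis; it does not threaten the trial's main conclusion.

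**What to change.** Before database lock, as an analysis change only:

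1. Add INR and aPTT rows to SAP 13.1 for the TEMAV table, taken from the CTCAE version the appendix already cites. The documents do not reproduce those grades, so the sponsor must confirm them at source. If coagulation is deliberately left ungraded, say so in SAP 5.6.3.
2. In SAP 5.6.3, add a shift of INR ≤1.6 / >1.6, the SAP's own baseline category, from baseline to Procedure Day and to Visit 6 by treatment group.
3. To cover the ceiling in that shift, summarise the maximum post-baseline change in INR among subjects already above 1.6 at baseline, by treatment group.
4. Note plasma or vitamin K use alongside items 2 and 3.

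Whether the expedited-reporting rule in protocol 9.5.4.3 should also apply to coagulation, and whether the 2-grade rule in 9.5.1.5 already does, is for the sponsor to reconcile across those sections and Appendix 1.

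The cost is two appendix rows, one shift table and one summary on data already scheduled for collection. The downside is a few more abnormalities to tabulate, and that plasma or vitamin K can alter post-baseline INR, so these displays need to be read with that treatment in view.
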